In- and exclusion criteria for trial sites (practices)	
Inclusion criteria
 
 - General practice cares for patients covered by statutory health insurance and is active in primary care - Specialist doctor for general practice or internal medicine, or doctor with no specialist field. - Practice has internet access - Investigator's agreement to fulfil the contractual obligations arising from the trial - Investigator's agreement to the training of a HCA from the practice for the intervention, as required by the trial 
Exclusion criteria
 
 - Practice focuses on unconventional medical treatments - Practice focuses on special indications (e.g. HIV)
In- and exclusion criteria for patients	
Inclusion criteria:
 
 - Age ≥ 60 and - ≥ 3 chronic diseases affecting ≥ 2 organ systems, requiring pharmaceutical treatment and - ≥ 5 long-term prescriptions with systemic effects and - Health care provided by GP (at least one contact in most recent quarter) and - Patient is legally competent to sign any documents and - Ability to understand and participate in trial of own free will, to fill out questionnaires and participate in telephone interviews as well as - Written informed consent to participate in trial 
Exclusion criteria:
 
 - Diseases cause life expectancy of < 12 months - Abuse of alcohol or illegal drugs and visible clinical signs or symptoms thereof - Cognitive disability that prevents trial participation (MMSE < 26) - emotional stress that prevents participation in trial - Participation in a clinical investigation within the last 30 days
Outcomes	
Primary outcome: difference in Medication Appropriateness Index (MAI)-Score 6 months from baseline minus baseline (MAI T1–T0)
 
Secondary outcomes: MAI T2-T0 and the difference in the following scores 6 and 9 months from baseline minus baseline (T1-T0 and T2-T0): EQ-5D, VES-13, all cause hospitalisation, medication adherence (observed: AS, DS, DoS, RS, self-reported: Morisky-Score), MRCI, BMQ, pain assessment (grade of severity of chronic pain in accordance with M. von Korff, J. Ormel et al. 1992), satisfaction with shared decision making (MSH), patient's future expectation, expected / desired lifetime duration, cognitive dysfunction (VFT), depression (GDS)

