8.1.2 Secondary Outcomes

(1) Change in the appropriateness of prescriptions after 9 months follow-up measured as the difference in the Medication Appropriateness Index (MAI)-Score 9 months from baseline minus baseline (MAI T2–T0): To study late intervention effects a second interval will be measured for the medication appropriateness at T2 (9 months after baseline). Furthermore, treatment effects on each MAI item will be determined.

The following parameters will be determined in order to identify treatment effects on patient related outcomes:

(2) Change in generic health related quality of life measured as the difference in the EQ-5D-Score^{39,40} 6 months from baseline minus baseline (T1–T0) and 9 months from baseline minus baseline (T2–T0): To ascertain whether the intervention improves the generic health related quality of life the EuroQuoL (EQ-5D) will be used.^{39,40} The EQ-5D was feasible in the pilot study and detects even relatively small changes.^{41,42}

(3) Change in functional disability measured as the difference in the VES-13-Score⁴³ 6 months from baseline minus baseline (T1–T0) and 9 months from baseline minus baseline (T2–T0): To ascertain whether the intervention improves functional disability, the activities of daily living will be assessed. In the pilot study the WHO DAS-II was found not to be feasible. In the main study the Vulnerable Elderly Survey, 13 items (VES-13) will be used.⁴³ The VES-13 predicts death and functional decline in vulnerable elderly patients,⁴³⁻⁴⁵ encompasses physical and instrumental activities of daily living and is feasible to use (pers. comm. Dr. [name], geriatrician, VES-13 use in the German PRISCUS-project; pers. comm. [name]: VES-13 use in the Maastricht multimorbidity project).

(4) Change in all cause hospitalisation: To ascertain whether the intervention improves all cause hospitalisation of patients, hospital days are counted irrespectively of reasons for admission.

(5) Change in medication adherence: To determine whether the intervention improves the medication adherence the following outcomes will be measured:

- Change in observed adherence measured as the difference between intake (*patient's interview*) and prescribed medication (CRF reported by physician's) 6 months from baseline minus baseline (T1–T0) and 9 months from baseline minus baseline (T1–T0)

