- Discrepancy score, DS (Sum of all differences in drug, time of intake, frequency and dose) / Sum of all prescriptions, $AS < 0.8$ or $> 0.2 = 1$
- Drug Score (DS, Sum of all drugs taken/sum of all prescriptions), $DS < 0.8$ or $DS > 1.2 = 1$ ⁴⁶
- Dose Score, (DoS, Sum of all daily doses taken/sum of all prescriptions), $DoS < 0.8$ or $DoS > 1.2 = 1$ ⁴⁶
- Regimen Score (RS, actual frequency of intake per day / prescribed frequency per day), $RS < 0.8$ or $DS > 1. = 1$ ⁴⁶
- Change in self-reported adherence measured as the difference in the Morisky-Score⁴⁷ 6 months from baseline minus baseline (T1–T0) and 9 months from baseline minus baseline (T2–T0)

5) Change in perceived future life expectancy reflects concepts of will to life or years of desired life [YDL] measured as the difference of the three items future expectation / expected lifetime duration / desired lifetime duration in the interval 6 months from baseline minus baseline (T1–T0) and 9 months from baseline minus baseline (T2–T0): Desired and expected life time duration are considered to be sensitive for personal experiences and scientific influences,⁴⁸ as well as indicating well being and positive life evaluation.⁴⁹ Moreover it is argued that YDL itself reflects mortality on the long run. Thus, if our intervention effects change in YDL, one might argue that participants consider the intervention as relevant in relation to their own life expectancy and life quality.

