12.2 Statistical hypotheses, methods, and analyses

The primary objective of this study is to determine the effectiveness of a complex intervention compared to usual care in multimorbid elderly patients, and to show that the complex intervention improves the appropriateness of prescriptions, as compared to usual care. The primary efficacy endpoint is the change in MAI score from baseline (T0) to 6 months after baseline (T1), i.e. the difference MAI T1–T0. The study objective will be statistically formulated as a test of the null hypothesis $H_0: \mu_1 = \mu_2$ (the mean difference MAI T1–T0 is equal in the two groups) against the alternative hypothesis $H_1: \mu_1 \neq \mu_2$ (the mean MAI T1–T0 are different in the two groups). The null hypothesis will be tested at the two-sided significance level of $\alpha=0.05$.

Because of the cluster randomisation, the primary efficacy analysis will use a multilevel regression approach with patients at level one and practices at level two. The primary model will include treatment group as fixed factor and practice as random factor. The results will be presented as the mean between-group difference in MAI T1–T0 with the corresponding 95% confidence interval. The associated Cohen's effect size d will be calculated. In addition, the practice related intraclass correlation coefficient (ICC) will be estimated. To support the primary analysis, all potentially relevant baseline characteristics at practice level (e.g. practice status) and baseline characteristics at patient level (e.g. MAI score at T0) will be added as covariates to the model in sensitivity analyses. Further sensitivity analysis of the primary endpoint will include an unadjusted two-sample t -test on change in MAI from baseline to 6 months after baseline. Results from these sensitivity analyses will serve to explain and interpret the results of the primary analysis.

The primary analysis will be performed adhering to the intention-to-treat principle. An additional sensitivity analysis will be conducted on a per-protocol analysis set.

Baseline characteristics of participating practices and patients will be described by treatment arm. Categorical data will be presented as frequencies and percentages. For continuous data, N, mean, standard deviation, median, inter-quartile range (IQR), minimum, and maximum will be provided.

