The statistical analyses of the secondary endpoints will use the same multilevel approach as the primary analysis. All statistical tests will be two-sided at the significance level of $\alpha=0.05$. Because no adjustments for multiple endpoints are planned, findings will be interpreted with caution in view of the number of statistical tests undertaken. Only the result of the primary efficacy analysis will be interpreted in a confirmatory manner. Confirmatory subgroup analyses are not planned. No interim analysis with regard to efficacy will be done.

A complete case analysis will be performed. If any practices or patients are lost to follow-up, analyses will be done replacing the missing follow-up data with the last available or baseline data carried forward for that practice or patient.

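### Secondary outcomes such as hospital days, adherence flags and pain grades are analysed as change from baseline without a baseline covariate, which costs precision when baseline and follow-up are weakly correlated

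*Protocol*

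**What the plan says.** Section 12.2 describes the primary model: "The primary model will include treatment group as fixed factor and practice as random factor". The outcome is the MAI difference T1–T0, and "The results will be presented as the mean between-group difference in MAI T1–T0 with the corresponding 95% confidence interval". Baseline values have a supporting role only: "baseline characteristics at patient level (e.g. MAI score at T0) will be added as covariates to the model in sensitivity analyses". That sentence concerns the primary endpoint. For everything else, section 12.2 states: "The statistical analyses of the secondary endpoints will use the same multilevel approach as the primary analysis".

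The Synopsis defines the secondary outcomes, beyond the MAI at nine months, as "the difference in the following scores 6 and 9 months from baseline minus baseline (T1-T0 and T2-T0". Its list includes all-cause hospitalisation, observed and self-reported adherence, and pain. Three types matter here:

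- **Hospitalisation** (8.1.2): "hospital days are counted irrespectively of reasons for admission", so it is a day count.
- **Observed adherence** (8.1.2): ratio scores, each followed by a rule that codes out-of-range values as 1. The Drug Score, for example, is "Sum of all drugs taken/sum of all prescriptions", coded 1 below 0.8 or above 1.2.
- **Pain** (8.1.3): two numeric scores, disability points and the resulting severity grades, all taken as differences.

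The opening of section 12 leaves the detailed methods to an SAP. Section 12.2 reserves confirmatory interpretation for the primary analysis and asks for caution with the rest.

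**The concern.** Subtracting baseline helps only as far as baseline predicts follow-up. If it predicts poorly, subtraction adds the baseline noise to the follow-up noise. Hospital days, a threshold flag and a coarse grade are outcomes for which a weak correlation is plausible.

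The difference is also awkward as a quantity. Two 0/1 flags give −1, 0 or 1, and two day counts can give a negative number. Neither is a binary or count outcome, so an SAP that keeps the protocol's definitions cannot repair this by choosing another link function.

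Adherence and all-cause hospitalisation are named secondary objectives in section 3. Section 8.1.3 uses pain as a surrogate for under-treatment, to detect a possible harm of reducing polypharmacy. Wide intervals on these outcomes would leave the questions open, although the T0 value that could narrow them is collected anyway.

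**Working it through.** **The plan's own figure.** The protocol states no power for any secondary outcome, so only the primary sample size can be reproduced. Inputs from section 12.3: d = 0.3, ICC 0.03, 7 patients per practice, two-sided alpha 0.05, power 0.80.

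- Design effect: 1 + (7 − 1) × 0.03 = 1.18.
- With 31 practices (217 patients) per arm, the non-centrality is 0.3 × √(217 / (2 × 1.18)) = 2.88.
- A t-test with 2 × (31 − 1) = 60 degrees of freedom then has power 0.808. With 30 practices per arm it is 0.795.

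The stated 31 practices and 217 patients per arm are therefore reproduced, and this size is used below.

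**Cost of the unadjusted change score.** Let the outcome have variance σ² at both visits and baseline–follow-up correlation rho.

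- Change score: variance 2σ²(1 − rho).
- Follow-up adjusted for baseline: residual variance σ²(1 − rho²).
- Ratio: 2(1 − rho) / (1 − rho²) = 2 / (1 + rho).

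An adjusted analysis with 80% power has an expected z of 1.960 + 0.842 = 2.802. The change score has 2.802 / √ratio, and its power is Φ(2.802 / √ratio − 1.960).

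| rho (assumed) | Variance ratio | Power of change score |
|---|---|---|
| 0 | 2.00 | 51% |
| 0.3 | 1.54 | 62% |
| 0.5 | 1.33 | 68% |
| 0.7 | 1.18 | 73% |
| 0.8 | 1.11 | 76% |

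The protocol gives no rho for any secondary outcome. Section 12.3 takes zero for the MAI, as a conservative sizing assumption. That shows the range worth considering and is not an estimate for these outcomes.

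**Simulation by outcome type.** The set-up was 2 × 31 practices of 7, latent ICC 0.03, 2,000 runs per scenario, and cluster-robust tests in place of the random-intercept fit. All rates, effects and correlations are assumptions. Here rho is the correlation of the underlying normal variable.

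| Outcome (assumed effect) | rho | Change, linear | Adjusted, linear | Adjusted, suited to type |
|---|---|---|---|---|
| 0/1 flag (30% v 18%) | 0 | 0.48 | 0.80 | 0.80 (logistic) |
| | 0.3 | 0.54 | 0.81 | 0.81 |
| | 0.6 | 0.69 | 0.86 | 0.86 |
| | 0.8 | 0.84 | 0.92 | 0.92 |
| 5 grades (shift 0.3 SD) | 0 | 0.48 | 0.78 | 0.78 (ranks) |
| | 0.3 | 0.58 | 0.79 | 0.79 |
| | 0.6 | 0.81 | 0.89 | 0.89 |
| | 0.8 | 0.97 | 0.98 | 0.99 |
| Hospital days (20% v 10% admitted, mean stay 10, skewed) | 0 | 0.24 | 0.52 | 0.50 (log-linear count) |
| | 0.3 | 0.27 | 0.52 | 0.51 |
| | 0.6 | 0.31 | 0.54 | 0.53 |

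The step from the third column to the fourth, which adds the baseline covariate, accounts for the loss: 2 to 30 points for grades, 8 to 32 for flags, and 21 to 28 for days (the last range covers either adjusted model). The step from the fourth column to the fifth, which changes the model type, moves power by less than 2 points. With no true effect, the change-score test rejected in 4.4% to 5.7% of runs, so its type I error is sound.

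**The case against.** The strongest reply is that the protocol never calls the secondary model linear. It speaks of a multilevel approach, states the mean difference for the MAI only, and leaves detail to an SAP that is not shown. A generalised model per outcome would fit those words. This stands: a reader might infer that a linear model is laid down for counts, flags and grades, and the text does not go that far. What the protocol does fix is the difference as the outcome and a model without baseline, and a choice of link in the SAP changes neither.

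Second, it is not settled that the 0/1 flags are what will be analysed. Section 8.1.2 gives both ratio and flag, and pain also has numeric scores. This stands too, so the point about flags is conditional. Analysing the ratios is not a clean escape, however. One patient moving from 0.7 to 1.0 and another from 1.3 to 1.0 both come into range, yet their changes of +0.3 and −0.3 cancel in a mean.

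Third, under randomisation the change score is unbiased, the difference in mean change of a flag estimates a risk difference, and a difference in mean hospital days can be read. That is fair. The issue is precision and clarity, not validity. The interpretation problem is greatest for grades, whose steps a mean treats as equal.

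**Conclusion.** The point holds as one of efficiency and interpretability. The protocol defines hospital days, adherence and pain grades as follow-up minus baseline and analyses them without a baseline covariate. If an adjusted analysis would have 80% power, the change score has between 51% (rho = 0) and 76% (rho = 0.8), assuming equal variances at both visits. Where in that range each outcome falls cannot be determined from the protocol. At high correlation the loss is small: 2 to 8 points for grades at rho 0.6 to 0.8 in the simulation.

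Three stronger conclusions are not supported:

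- A reader might infer that linearity causes the loss. With baseline adjustment held fixed, the model type made almost no difference to power.
- A reader might infer that a missed effect is likely. The protocol gives no rates, effects or correlations from which to say so.
- A reader might set change in hospital days against a logistic analysis of any admission and find a far wider gap. That swaps the endpoint. Like for like, under the assumed rates, the figures are 0.24–0.31 against 0.50–0.54.

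The primary result is untouched, type I error is preserved, and the secondary results are not confirmatory. The change is still worth making, because it uses data already collected.

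**What to change.** In section 12.2, state that each secondary outcome is analysed as its T1 value and its T2 value, not as the difference, with the T0 value as covariate and practice as random effect. Name the model by outcome type:

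- linear for continuous scores;
- logistic for 0/1 adherence flags, if these are the analysed variable;
- a count model for hospital days;
- proportional odds for pain grades.

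Say in section 8.1.2 whether the adherence ratios or the flags are analysed, and align the outcome definitions in the Synopsis, 8.1.2 and 8.1.3.

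The cost is protocol and SAP wording. No extra patients or visits are needed: Table 1 already schedules the source data at T0, and section 4 places disclosure of allocation after each practice's baseline documentation is complete. The downside is that odds ratios or rate ratios replace a common mean-difference format for some outcomes.

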12.3 Sample size

Sample size was calculated using the primary endpoint, the change in MAI score from baseline (T0) to 6 months after baseline (T1), i.e. MAI T1–T0. Because high MAI scores indicate inappropriate prescriptions, a negative difference MAI T1–T0 indicates an improvement in the appropriateness of prescriptions for the target population. The MAI T1–T0 difference is assumed to be normally distributed in each treatment arm population and the variances of the group specific differences T1–T0 are assumed to be equal. In the preliminary analysis of PRIMUM pilot with a total of 60 patients from 12 practices, a mean MAI of 4.2 was observed at baseline. Three months later (i.e. 6 weeks after the intervention), the MAI in the intervention group decreased by 0.9 units, while the MAI in the control group decreased by 0.5 units. Thus, the resulting between-group difference was 0.4 in favour of the complex intervention. In a previous study of a similar patient population, between-group differences of 3 and 4 for changes in MAI from baseline to 3 and 12 months after randomisation were reported.³² However, the intervention in that study was even more intense than the intervention planned in PRIMUM. Thus, in the present study, a difference in the change values (MAI T1–T0) of at least 2 units between the treatment groups will be considered clinically relevant. In the PRIMUM pilot study, a pooled standard deviation of the MAI T1–T0 difference of 5.2 was observed. However, T1 was defined as 3 months from baseline, whereas in the present study, T1 is measured 6 months after baseline. Consequently, a greater standard deviation is expected for the MAI T1–T0 difference. Using the conservative assumption that the MAI scores at T0 and T1 are uncorrelated, we expect a standard deviation for MAI change of approximately 6 units. With this standard deviation, a between-group difference of 2 units corresponds to Cohen's effect size of $d=0.3$ and represents a small effect size.⁶³ Assuming an intraclass correlation coefficient (ICC) of 0.03 at practice level (which is also a conservative assumption because the ICC is assumed to be 0.01 in general practice setting⁶⁴) and assuming an average cluster size of 7 patients, we estimated a design effect of $DEFF = 1 + (7 - 1) \times 0.03 = 1.18$. Taking this design effect into consideration, a total of 62 practices and 434 patients (31 practices and 217 patients per treatment arm) will be required to detect a Cohen's d of 0.3 with a power of $1-\beta = 0.80$ using a two-sample t -test at a two-sided significance level of $\alpha=0.05$. The sample size calculation was performed using NCSS PASS 2008,

Inequality Tests for Two Means in a Cluster Randomised Trial. Assuming a drop-out rate of approximately 10%, the sample size was adjusted to a total of 70 practices and 490 patients (35 practices and 245 patients in each treatment group).

13 ETHICAL AND REGULATORY REQUIREMENTS

13.1 Ethical fundamentals

The project will be carried out in conformation with the Medical Association's code of conduct and good clinical practice (GPC) in line with the World Medical Association Declaration of Helsinki⁶⁵. The trial will be checked and approved by the ethics commission of Frankfurt University Hospital. The original vote by the ethics commission will be kept in the Trial Master File at the Institute for General Practice. In addition, every participating practice will receive a copy to be kept in the investigator's file.

The voluntary participation of doctors and patients in the trial will be recorded in writing following an informed decision to do so. Patients in intervention practices who do not wish to participate will be treated without intervention and in accordance with usual care.

Data protection will be guaranteed for all person-related data: the data will be collected and stored separately from the other individual data in the trial, and deleted at the end of it. Participating patients will be separately informed about data protection in the trial and will give their consent by signing and dating a declaration to that effect. For data analyses, patient identifiers will be kept confidential and the data stored in a separate data base from the personalized one. The trial team are the only persons with access to trial data. Practice teams are also bound by the legal requirement to treat data confidentially.

The present trial will take ICH-GCP criteria into account, and all participants have undertaken an obligation to respect the Declaration of Helsinki and its amendments

The Ethics Commission is to be informed of all changes to the protocol and its renewed approval is to be sought if necessary.

Changes linked to the following points are regarded as requiring renewed approval:

- Necessary changes to the therapy regime, in particular:
 1. Intensification of intervention that is a burden to the patient or could be felt to be a burden by him,
 2. Reduction in intensity of intervention, in view of which a discussion on the likelihood of success must take place,
 3. Inclusion of further elements in the intervention program about which the patient has not yet been informed,
 4. Changes in the therapy regime of the control arm,
 5. Revision in the risk estimate for participating patients;
 6. Additional examinations, data collection or analyses that necessitate a change in patient information and/or the consent form.

13.2 Subsequent changes to protocol

Changes to protocol may only occur with the prior agreement of all co-operation partners. All participating practices in the trial must be informed of such changes in written form. Changes must be dated and deposited in the Trial Master File.

If in the course of the trial it becomes clear that changes or additions must be made to the present trial protocol, then these must be laid down in the form of an amendment and signed by the principal investigator, the investigators and by those responsible for approving the trial protocol.

Changes to the timetable that may influence the safety of trial participants or the scientific analysis of the trial necessitate renewed approval by the responsible Ethics Commission. The Commission is to be informed of changes to the trial protocol that occur solely for logistical or administrative reasons.

